### 10.1. Extent of Exposure

Study Drug Exposure, study duration and cumulative dose will be summarized for each treatment group and overall, and will also be listed.

### 10.2. Treatment Compliance

Overall treatment compliance (%) is defined as number of tablets taken during the complete treatment period / number of tablets expected to be taken during the complete treatment period \* 100. Overall compliance (%) and classified overall compliance (<80%, 80-120%, >120%) will be summarized. The number of tablets (study medication) dispensed, returned, lost/damaged/missed, overall compliance and overall classified compliance will be listed.

### 10.3. Adverse Events (AEs)

All reported AEs will be coded using the most recent version of Medical Dictionary for Regulatory Activities (MedDRA). The incidence of TEAEs (events with onset dates on or after the start of the study drug) will be included in incidence tables. Events with missing onset dates will be included as treatment-emergent unless an incomplete date clearly indicates that the event started prior to the first study drug administration. If a subject experiences more than 1 occurrence of the same AE, the occurrence with the greatest severity and the closest association with the study drug will be used in the summary tables. Serious AEs, AEs causing discontinuation and AESIs will be tabulated. All AEs will be listed by subject, along with information regarding onset, duration, relationship and severity to study drug, action taken with study drug, treatment of event, and outcome.

Adverse events (AEs) will be coded using MedDRA 22.0 or higher version.

Events that occur after a subject provides informed consent but before the time of the first dose of study drug will be considered non treatment-emergent AEs. Treatment-emergent AEs are defined as events that are newly occurring or worsening from the time of the first dose of study drug.

Missing dates will not be imputed. However, the following table will be utilized to categorize TEAEs.

AE Start Date	AE End Date	Rule on AE End Date	Rule on AE Start Date	TEAE
Not missing			AE Start Date < Treatment Start Date	N
			AE Start Date ≥ Treatment Start Date	Y
Partly missing	Not missing	AE End Date < Treatment Start Date		N
		AE End Date ≥ Treatment Start Date	non missing part of AE Start Date < Treatment Start Date	N
			non missing part of AE Start Date	Y

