Patients with Na-2 must have a comparable history of irrepressible need to sleep or daytime lapses into sleep for at least 3 months, identical criteria based upon MSLT and nocturnal PSG, but do not have a clinical history of cataplexy or data based upon CSF hypocretin-1 concentrations which are incompatible with the diagnosis. For both conditions, eligibility criteria mimic those frequently associated with interventional studies in narcolepsy and reduce diagnostic confounders related to medical condition such as obstructive sleep apnea, and psychiatric disorders including chronic fatigue syndrome, depression, bipolar affective disorder, malingering, and substance use disorder. Idiopathic hypersomnia must be excluded by the pre-existing diagnostic evaluation [Broughton et al, 1997].

SUVN-G3031 in this study is being evaluated as a monotherapy; patients will require washout from current narcolepsy therapies for both EDS and cataplexy. Washout period will occur within a maximum 28-day screening period to allow for minimum drug free period of  $\geq 7$  days for all stimulants targeting EDS, and  $\geq 14$  days for all agents targeting cataplexy prior to randomization and baseline assessments. The 28-day screening period allows a window of drug withdraw to be completed safely at the discretion of the Investigator.

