## 12.7 Adverse Events

### 12.7.1 Adverse Events

An AE is any symptom, physical sign, syndrome, or disease that either emerges after the patient signs the ICF or, if present at Screening, worsens after signing the ICF, regardless of the suspected cause of the event. All medical and psychiatric conditions (except those related to the indication under study) present at Screening will be documented in the medical history eCRF. Changes in these conditions and new symptoms, physical signs, syndromes, or diseases should be noted on the AE eCRF during the rest of the study. Clinically significant laboratory abnormalities should also be recorded as AEs. Surgical procedures that were planned before the patient enrolled in the study are not considered AEs if the conditions were known before study inclusion; the medical condition should be reported in the patient's medical history.

Patients will be instructed to report AEs at each study visit. All AEs are to be followed up until resolution or a stable clinical endpoint is reached.

Each AE is to be documented on the eCRF with reference to date of onset, duration, frequency, severity, relationship to study drug, action taken with study drug, treatment of event, and outcome. Furthermore, each AE is to be classified as being serious or nonserious. Changes in AEs and resolution dates are to be documented on the eCRF.

For the purposes of this study, the period of observation for collection of AEs extends from the time the patient gives informed consent until the follow-up visit. Follow-up of the AE, even after the date of therapy discontinuation, is required if the AE persists until the event resolves or stabilizes at a level acceptable to the Investigator.

When changes in the intensity of an AE occur more frequently than once a day, the maximum intensity for the event should be noted. If the intensity category changes over a number of days, then those changes should be recorded separately (with distinct onset dates).

The severity of AEs will be graded according to [Table 3](#).

Specific guidelines for classifying AEs by intensity and relationship to study drug are given in [Table 3](#) and [Table 4](#).

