## Statistical Analysis Plan

Sponsor: Suven Life Sciences; Protocol No.: CTP2S13031H3

AE Start Date	AE End Date	Rule on AE End Date	Rule on AE Start Date	TEAE
	Partly missing	non missing part of AE End Date < Treatment Start Date	≥ Treatment Start Date	N
		non missing part of AE End Date ≥ Treatment Start Date	non missing part of AE Start Date < Treatment Start Date	N
	Totally Missing or Ongoing		non missing part of AE Start Date ≥ Treatment Start Date	Y
			non missing part of AE Start Date < Treatment Start Date	N
	Totally Missing		non missing part of AE Start Date ≥ Treatment Start Date	Y
		AE End Date < Treatment Start Date		N
	Not missing	AE End Date ≥ Treatment Start Date		Y
		non missing part of AE End Date < Treatment Start Date		N
	Partly missing	non missing part of AE End Date ≥ Treatment Start Date		Y
	Totally Missing or Ongoing			

An overall summary of AEs and TEAEs will show the number and percentage of subjects (and the corresponding number of TEAEs) by treatment group

- any AEs
- any TEAE
- any TEAE by severity
- any related TEAE
- any TEAE leading to treatment discontinuation
- any SAE
- any related SAEs
- any AESIs
- any TEAE leading to death

Summary tables by system organ class and preferred term will be provided for treatment group and overall for

- TEAEs
- TEAEs by maximum severity
- TEAEs by maximum relationship to study treatment
- Treatment-related TEAEs
- Serious TEAEs
- TEAEs leading to withdrawal
- AEs of special interest (AESI)

As AESI the following AEs (after start of study treatment) will be considered:

- Vivid and/or unpleasant dreams
- Difficulty initiating or maintaining sleep

The summaries will be produced on the Safety Analysis Population.

Separate listings will be provided in the tables section for

- any SAE

This document is confidential.

- any fatal AE
- any AE leading to treatment discontinuation

All TEAEs for each subject, including multiple occurrences of the same event, will be presented for all randomized subjects. In a separate listing all non-TEAEs of randomized subjects will be provided.

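### The SAP 10.3 table sets the TEAE flag by start date alone when dates are complete, so a pre-dose adverse event that eases after first dose is flagged against the SAP's own definition

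*SAP*

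**What the plan says.** **Recording.** Protocol 12.7.1 tells sites: "If the intensity category changes over a number of days, then those changes should be recorded separately (with distinct onset dates". It does not restrict this to worsening. Faster fluctuation is handled differently: "When changes in the intensity of an AE occur more frequently than once a day, the maximum intensity for the event should be noted". Recording starts well before dosing, since "the period of observation for collection of AEs extends from the time the patient gives informed consent until the follow-up visit".

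**Before first dose.** Protocol 7.2.1 says: "Washout period will occur within a maximum 28-day screening period to allow for minimum drug free period of" at least 7 days for stimulants and at least 14 days for cataplexy agents. Adverse events can therefore start, and be recorded, before Day 1.

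**Definition.** SAP 10.3 gives two statements. One is by date: "The incidence of TEAEs (events with onset dates on or after the start of the study drug) will be included in incidence tables". The other is by substance: "Treatment-emergent AEs are defined as events that are newly occurring or worsening from the time of the first dose of study drug".

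**Flag.** The rule to be programmed is a table, introduced by: "Missing dates will not be imputed. However, the following table will be utilized to categorize TEAEs". Its first rows cover complete start dates: earlier than treatment start gives N, on or after gives Y. End dates are used only when the start date is partly or wholly missing. No row compares severity or links records of one episode.

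**Counting.** In the summary tables a subject with repeated occurrences of the same event is represented by one of them, the most severe and most closely related. The overall summary also gives the number and percentage of subjects "and the corresponding number of TEAEs) by treatment group". Nothing says how split records enter that event count.

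**The concern.** The recording rule and the flagging rule are each workable, but they do not fit together. The protocol creates a new onset date whenever intensity steps up or down over days. The SAP table reads any onset date from first dose on as treatment-emergent. An event that predates treatment and is resolving then appears as a TEAE, which the SAP's definition excludes.

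Two outputs are affected, in different ways. Subject-level TEAE incidence can gain patients who have no TEAE by definition. Event totals can count one episode several times. SAP 10.3 also identifies AESIs by timing (after treatment start), so the same false flag can reach the AESI table. Safety and tolerability are in the study title, so these tables are among the main results.

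**Working it through.** The plan gives no figure on this point to reproduce. The check applies the SAP table to records split as protocol 12.7.1 requires and compares the result with the SAP's definition. Day 1 is first dose (SAP 6.2.9). The days and severities below are invented for the check.

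| Case | Records | TEAE records by the table | TEAE episodes by the definition |
|---|---|---|---|
| A. Pre-dose event eases | Day -5 moderate, Day 2 mild | 1 | 0 |
| B. Pre-dose event worsens | Day -5 mild, Day 2 moderate | 1 | 1 |
| C. Event starts on treatment | Day 3 mild, Day 4 moderate, Day 6 mild | 3 | 1 |
| D. Pre-dose event eases in two steps | Day -4 severe, Day 1 moderate, Day 3 mild | 2 | 0 |

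- Case B shows what the split records do well: they give a date-only rule a post-dose onset by which to catch a worsening. Cases A and D show that the same mechanism catches improvement.
- In A and D the patient enters subject-level incidence. The one-occurrence rule does not help, because it chooses among flagged records and the easing record is flagged.
- In C the patient counts once by preferred term under either rule. Only the event total (3 against 1) and the listing are multiplied.

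**Illustrative size at subject level.** Let p be the share of patients with a genuine TEAE and q the share with a pre-dose event that eases after first dose. The documents give neither. Assume p = 20% to 40%, q = 5% to 30%, and independence. Then observed incidence = p + (1 - p)q, an increase of (1 - p)q.

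- Low end: (1 - 0.40) x 0.05 = 0.03. Of 38 per arm (initial plan): 38 x 0.03 = 1.1 patients. Of 57 per arm (re-estimated maximum, SAP 3.6): 57 x 0.03 = 1.7.
- High end: (1 - 0.20) x 0.30 = 0.24. Of 38: 9.1 patients. Of 57: 13.7.

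**Between-arm effect, same formula, assumed inputs.**

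- True rates 30% and 15%, q = 10% in both arms: 0.30 + 0.70 x 0.10 = 37.0% and 0.15 + 0.85 x 0.10 = 23.5%. The difference falls from 15 to 13.5 points, a factor of 1 - q.
- True rate 30% in both arms, q = 20% in one and 10% in the other: 0.30 + 0.70 x 0.20 = 44% against 0.30 + 0.70 x 0.10 = 37%. A 7-point difference appears where none exists, and its sign depends on which arm has the larger q.

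The result can be dilution, no change, or a spurious difference in either direction. Which of these applies depends on q in each arm.

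**The case against.** **The SAP already has the right concept.** Its definition excludes improvement, and the table's introduction suggests that it is mainly for incomplete dates. This stands in part: the defect is a conflict between definition and algorithm, not a missing idea. But the table has explicit rows for complete start dates, and the date-only sentence in SAP 10.3 agrees with them, as does protocol 14.4.1. A programmer who follows the table gets cases A and D wrong.

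**Few carry-over events may be recorded as AEs.** Protocol 12.1 treats conditions present at consent and up to first dosing as concomitant, and asks for worsening to be recorded. This points conditions already present at consent towards medical history. It does not clearly cover events that first arise between consent and first dose, which 12.7.1 collects and which SAP 10.3 expects, since it lists non-treatment-emergent AEs separately.

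**Safety results are descriptive.** This is true. No hypothesis test is affected, which limits the consequence to interpretation.

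**Linking could merge separate episodes**, for example unpleasant dreams on successive nights. This is a fair point, and the fix has to guard against it.

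A reader might also infer more than the documents support:

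- That every change in intensity makes a new record. It does not: changes more often than daily are noted once, at maximum intensity.
- That the multiple counting reaches subject incidence by preferred term. It does not, because of the one-occurrence rule.
- That every patient goes through washout. Newly diagnosed patients are eligible (protocol 8.1), and protocol 9.6.1 applies washout to those taking the listed drugs.
- That the sleep-related AESI is diluted, or the placebo background raised, by a known amount. Nothing in the documents says how often such events are ongoing at first dose or how they evolve by arm.

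**Conclusion.** The point holds as an inconsistency inside SAP 10.3, exposed by the protocol's recording rule. For complete dates, the table flags as treatment-emergent a pre-dose event that eases after first dose, although the definition in the same section excludes it. This rests on the text alone. Event totals are also inflated by split records of one episode.

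The size is unknown. The rise of 3 to 24 percentage points in any-TEAE incidence follows from assumed rates and independence. It shows the scale the rule could reach and is not a prediction. For a single preferred term or AESI only events of that type contribute, so the effect would be smaller. No direction of between-arm bias can be claimed. The correction should be made because it is cheap and brings the flag into line with the SAP's definition.

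**What to change.** In SAP 10.3:

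1. Link records that are intensity changes of one episode: same term, with the new record starting when the previous one ends. Records that are separate recurrences stay separate.
2. Flag the linked episode as a TEAE only if its first record starts on or after first dose, or a record from first dose on exceeds the last pre-dose severity. Using the last pre-dose value matches the general baseline definition in SAP 6.2.1.
3. Count each linked episode once, at maximum severity, in the event totals.
4. Apply the same rule to AESIs.
5. State that the new-or-worse definition governs where it and the date rule differ. The rows for incomplete dates can remain.

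The cost is a wording change and a short derivation step. Onset date, severity and resolution date are already collected for each AE under protocol 12.7.1, so no new data are needed. The small downside is the risk of merging truly separate episodes. The linkage rule must be written to prevent that, and linked records can be checked in the listing, which still shows every record.

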## Statistical Analysis Plan

Sponsor: Suven Life Sciences; Protocol No.: CTP2S13031H3

AE Start Date	AE End Date	Rule on AE End Date	Rule on AE Start Date	TEAE
	Partly missing	non missing part of AE End Date < Treatment Start Date	≥ Treatment Start Date	N
		non missing part of AE End Date ≥ Treatment Start Date	non missing part of AE Start Date < Treatment Start Date	N
	Totally Missing or Ongoing		non missing part of AE Start Date ≥ Treatment Start Date	Y
			non missing part of AE Start Date < Treatment Start Date	N
	Totally Missing		non missing part of AE Start Date ≥ Treatment Start Date	Y
		AE End Date < Treatment Start Date		N
	Not missing	AE End Date ≥ Treatment Start Date		Y
		non missing part of AE End Date < Treatment Start Date		N
	Partly missing	non missing part of AE End Date ≥ Treatment Start Date		Y
	Totally Missing or Ongoing			

An overall summary of AEs and TEAEs will show the number and percentage of subjects (and the corresponding number of TEAEs) by treatment group

- any AEs
- any TEAE
- any TEAE by severity
- any related TEAE
- any TEAE leading to treatment discontinuation
- any SAE
- any related SAEs
- any AESIs
- any TEAE leading to death

Summary tables by system organ class and preferred term will be provided for treatment group and overall for

- TEAEs
- TEAEs by maximum severity
- TEAEs by maximum relationship to study treatment
- Treatment-related TEAEs
- Serious TEAEs
- TEAEs leading to withdrawal
- AEs of special interest (AESI)

As AESI the following AEs (after start of study treatment) will be considered:

- Vivid and/or unpleasant dreams
- Difficulty initiating or maintaining sleep

The summaries will be produced on the Safety Analysis Population.

Separate listings will be provided in the tables section for

- any SAE

This document is confidential.

- any fatal AE
- any AE leading to treatment discontinuation

All TEAEs for each subject, including multiple occurrences of the same event, will be presented for all randomized subjects. In a separate listing all non-TEAEs of randomized subjects will be provided.

#### 10.4. Laboratory Evaluations

Descriptive statistics will be performed for those laboratory parameters on a continuous scale for actual values and change from baseline at each visit, by treatment. Categorical results for urinalysis will be summarized using frequency tabulations. Abnormal values for each analyte will be determined using reference ranges provided by the central laboratory. All laboratory results will be listed including unscheduled visits. Additionally, shift table of post-baseline to baseline of the values below normal range, within normal range and above normal range will be provided.

Dipstick urinalysis results evaluation (Normal, Abnormal Not Clinically Significant and Abnormal Clinically Significant) will be summarized at each protocol scheduled time point by treatment group using frequency tabulations. All abnormal laboratory values will be flagged in the listings.

The following table summarizes all laboratory parameters which will be assessed in the study.

Hematology	Serum Chemistry	Urine Analysis (Dipstick)
Hematocrit	Albumin	Appearance
Hemoglobin	Alanine aminotransferase	pH
Red blood cell count	Alkaline phosphatase	Protein
White blood cell count with differential	Aspartate aminotransferase	Glucose
Platelets	Blood urea nitrogen or urea	Ketone bodies
Red blood cell indices	Creatinine	Indicators of blood and white blood cells
	Electrolytes (sodium, potassium, chloride, calcium)	Specific gravity
	Gamma glutamyltransferase	Urobilinogen
	Glucose	Microscopic analysis will occur when dipstick indicates clinically significant changes in one of the above.
	Lactate dehydrogenase	
	Total bilirubin	
	Direct bilirubin	
	Uric acid	
	Follicle-stimulating hormone a	
	Thyroid stimulating hormone b	
Virology/Serology tests: Virology and Serology laboratory tests (i.e., Hepatitis B, Hepatitis C, and human immunodeficiency virus) will be completed at Screening.		
Pregnancy test: A pregnancy test will be performed on all women of childbearing potential at Screening, baseline, Day 7, Day 14, and follow-up. Additionally, a serum pregnancy test will also be performed at baseline.		
Urine drug screen: The following drugs will be tested for: barbiturates, benzodiazepines, cocaine, cannabinoids, methadone, methamphetamines, morphine/opiates, phencyclidine, and tricyclic antidepressants.		

a Serum follicle-stimulating hormone tests will be completed as necessary.

b Thyroid stimulating hormone tests will be completed at Investigator's discretion.

Women of childbearing potential (WOCBP) must have a negative pregnancy test at Screening, Baseline, and follow-up. After administration of study drug, any known cases of pregnancy in female subjects or female partners of male subjects will be reported until the subject completes or withdraws from the study.

A listing with pregnancy test results will be summarized for all randomized female subjects.

#### **10.5. Vital Signs**

Vital signs (body temperature, respiration rate, heart rate, and systolic and diastolic blood pressure measurements) will be evaluated at the visits indicated in the Schedule of Assessments. All vital signs will be measured after the subject has been resting in a sitting position for at least 5 minutes. Blood pressure measurements are to be taken in the same arm for the duration of the study. Body weight (without shoes) will be recorded whenever vital signs are recorded; height (without shoes) will be recorded at Screening only.

Vital signs and body weight will be summarised at each protocol scheduled time point by treatment group. Actual values and changes from baseline will be presented. Vital signs and body weight will be listed for all randomized subjects.

#### **10.6. Electrocardiogram (ECG)**

A frequency tabulation of ECG results evaluation (Normal, Abnormal Not Clinically Significant or Abnormal Clinically Significant) will be presented at each protocol scheduled time point, by treatment group at each time point. Additionally, a shift table of the overall ECG evaluation at the post-baseline visits compared to baseline will be provided.

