### **8.4 Study Withdrawal, Removal, and Replacement of Patients**

If a patient discontinues study treatment and is withdrawn from the study for any reason, the study site must immediately notify the medical monitor. The date and the reason for study discontinuation must be recorded on the electronic case report form (eCRF). Patients who complete or discontinue early from the study will be asked to return to the study site within 7 days of the last administration of study drug to complete the safety follow-up assessments as indicated in the Schedule of Assessments ([Table 1](#)).

Patients who want to discontinue early from the study (i.e., at the next visit), or who make a decision to withdraw during a scheduled visit, and who remain on study drug should complete

the rating scale/assessments indicated for that visit (Visit 2 or Visit 3) as well as the safety follow-up assessments according to the Schedule of Assessments ([Table 1](#)).

In the event that a patient discontinues prematurely from the study because of a TEAE or serious TEAE, the TEAE or serious TEAE will be followed until it resolves (returns to normal or baseline values) or stabilizes, or until it is judged by the Investigator to no longer be clinically significant.

Once a patient is withdrawn from the study, the patient may not re-enter the study. Care of the patient will return to their usual doctor.

A patient may voluntarily withdraw or be withdrawn from the study at any time for reasons including, but not limited to, the following:

- Unacceptable toxicity or AE.
- Clinically significant abnormal lab values:
  - Alanine aminotransferase (ALT) or aspartate aminotransferase (AST)  $\geq 8x$  upper limit of normal (ULN);
  - ALT or AST  $\geq 3x$  ULN and total bilirubin  $\geq 2x$  ULN at the same visit;
  - ALT or AST  $\geq 3x$  ULN with the appearance of symptoms indicating hepatitis (e.g., worsening fatigue, nausea, vomiting, right upper quadrant pain or tenderness, fever, rash, or eosinophilia).
- QT syndrome, Fridericia's formula corrected QT (QTcF) interval  $\geq 470$  ms (for male subjects) or  $\geq 480$  ms (for female subjects), or torsades de pointes. Abnormal results for ECGs should be confirmed with repeat ECG recordings to ensure reproducibility of the abnormality before withdrawing the subject from the study.
- A positive urinary drug screen at any visit.

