c Electrocardiograms should be obtained after the patient has been quiet and supine for approximately 3 minutes. An ECG will be captured at baseline (Day 0, Visit 1), and 3 h (±30 min) postdose on Days 7 and 14.

d Laboratory assessments are listed in [Table 2](#).

e Venipuncture for point estimates of the plasma concentration of SUVN-G3031 will be obtained at baseline (Day 0; blank), and on Day 7 (Visit 2) and Day 14 (Visit 3) at the estimated trough just prior to dosing and at the estimated maximum plasma concentration of SUVN-G3031 (3± 0.5 hours postdosing on Day 7 and Day 14) for a total of 5 samples.

f A serum pregnancy test will be completed at baseline (Day 0; Visit 1). Urine pregnancy tests will be completed at Screening, Baseline (Visit 1), Day 7 (Visit 2), Day 14 (Visit 3), and Day 21 (Safety Follow-up visit).

g A positive UDS at Screening can be repeated up to Day -1; however, a negative UDS is required prior to Day 0 (Baseline visit), and a second negative UDS is required on Day 0 (Baseline visit).

h Within the current study nocturnal overnight PSG will be completed at baseline (Day 0; Visit 1), Day 7 (Visit 2), and at Day 14 (Visit 3). Variables to be collected will include latency to persistent sleep in minutes (latency from lights-off to the first epoch of 20 consecutive epochs of any stage of sleep), number of arousals, number of awakenings, sleep efficiency, total sleep time in minutes, wake after sleep onset in minutes, percentage of time in stage 1, 2, 3, 4, REM sleep percentage, REM sleep latency in minutes and periodically movements during sleep (N).

i    
 j Physicians will complete a CGI-S and CGI-C assessments for EDS rather than totally of illness. The CGI-S assessment will be completed first followed by CGI-C evaluation. The administrator of the CGI-S and CGI-C should remain consistent for each patient at each visit.

k ESS, PGI-C, CSSRS assessments will be completed in this order at the beginning of each evaluation day prior to start of first MWT session. Note: 2 distinct forms of CSSRS will be used: “Baseline-Screening” form will be used at Screening and “Since Last Visit” form will be used at subsequent visits.

l For the PGI-C, the patient will be asked to address the totality of experience on study medication, without attempts to demarcate between excessive daytime somnolence versus cataplexy.

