## **12.4 Electrocardiograms**

A 12-lead, resting ECG will be obtained at the visits indicated in the Schedule of Assessments ([Table 1](#)). The following parameters will be measured at a minimum: heart rate, PR, QRS, QT and Fridericia's correction of QT intervals. The same ECG machines should be used for each patient throughout the study.

At Screening, the Investigator will examine the ECG traces for signs of cardiac disease that could exclude the patient from the study. An assessment of normal or abnormal will be recorded; if the ECG is considered abnormal, the abnormality will be documented on the eCRF.

Electrocardiograms will be repeated if clinically significant abnormalities are observed or artifacts are present. A central cardiac laboratory will be used in this study.

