## 14 STATISTICAL ANALYSIS

A SAP will be prepared after the protocol is approved. This document will provide further details regarding the definition of analysis variables and analysis methodology to address all study objectives. The SAP will serve as a complement to the protocol and supersedes it in case of differences.

The statistical evaluation will be performed using SAS® software version 9.4 or higher (SAS Institute, Cary, NC). All data will be listed, and summary tables will be provided.

Summary statistics will be presented by treatment group. For continuous variables, data will be summarized with the number of patients (n), mean, SD, standard error of mean, median, minimum, and maximum by treatment group. For categorical variables, data will be tabulated with the number and proportion of patients for each category by treatment group.

An unblinded interim analysis is planned when approximately 50% of patients have completed 14 days of treatment (Visit 3 completed). This interim analysis is for the purpose of sample size re-estimation, and futility will not be examined. Interim analysis will occur under the supervision of an independently charted DMC. See [Section 7.1.4](#).

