#### **14.4.4     Electrocardiogram**

Change from baseline in the 12-Lead ECG results will be calculated and summarized along with the actual results for each scheduled visit. ECG data will also be listed.

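### SAP 10.6 specifies only categorical ECG tables and does not visibly carry over the protocol's summaries of actual values and change from baseline for ECG parameters, including QTcF

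*SAP*

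**What the plan says.** Protocol 14.4.4 sets the ECG analysis: "Change from baseline in the 12-Lead ECG results will be calculated and summarized along with the actual results for each scheduled visit". The statistical part of the synopsis makes the same commitment. Protocol 12.4 says what is measured: "The following parameters will be measured at a minimum: heart rate, PR, QRS, QT and Fridericia's correction of QT intervals".

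Table 1 of the protocol, footnote c, fixes the timing: "An ECG will be captured at baseline (Day 0, Visit 1), and 3 h (±30 min) postdose on Days 7 and 14". Footnote e places the post-dose PK sample in the same window of 3 ± 0.5 h, described as "at the estimated maximum plasma concentration of SUVN-G3031".

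SAP 10.6 contains two outputs and shows no blacked-out text. The first is "A frequency tabulation of ECG results evaluation (Normal, Abnormal Not Clinically Significant or Abnormal Clinically Significant) will be presented" at each scheduled time point by treatment group. The second is "a shift table of the overall ECG evaluation at the post-baseline visits compared to baseline will be provided".

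On precedence, the opening of protocol section 14 states: "The SAP will serve as a complement to the protocol and supersedes it in case of differences".

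**The concern.** ECG is a named safety endpoint in both documents. Numeric QTcF limits decide eligibility (protocol 8.2, criterion 7) and appear among the withdrawal reasons in protocol 8.4, under "QT syndrome, Fridericia's formula corrected QT (QTcF) interval". The on-treatment ECGs are timed to the estimated peak concentration. Yet the analysis text that takes precedence reports no interval at group level.

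A three-level rating and a shift table of that rating show movement between categories. They carry no information on movement within a category. A dose-related mean change in QTcF, PR or heart rate would therefore not appear in either table if it left patients in the same category. Detecting such a change is the usual purpose of a change-from-baseline table, and two active doses with a placebo arm make the comparison possible here.

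**Working it through.** The point is mainly textual, and the plan gives no figure to reproduce.

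**Step 1. Compare the safety analyses.**

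| Data | Protocol | SAP |
|---|---|---|
| Laboratory, continuous | raw scores and change, each visit (14.4.2) | actual values and change, each visit, plus shift table (10.4) |
| Vital signs | actual and change, each visit (14.4.3) | actual values and change (10.5) |
| ECG | actual and change, each visit (14.4.4) | rating frequencies and shift of rating (10.6) |

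Only the ECG row differs. In the laboratory row the shift table is added to the change summary, so a shift table is not this SAP's usual substitute for one.

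**Step 2. Can the 10.6 tables meet the 14.4.4 commitment?** No. An overall rating has no numeric change from baseline, and heart rate, PR, QRS, QT and QTcF are continuous.

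**Step 3. Does other visible SAP text supply the missing summaries?** SAP 6.1 gives default descriptive statistics, 6.2.3 defines change from baseline, and section 10 lists ECG parameters among the bases for safety. None of these calls for a summary of an ECG interval. Section 17 keeps a by-subject ECG listing (16.2.8.2.2).

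**Step 4. Count what is at issue.** The schedule has ECGs at Screening, Day 0, Day 7, Day 14 and Day 21. With the baseline of SAP 6.2.1 (last valid value before first dose), three visits are post-baseline. Five parameters × 3 visits = 15 change-from-baseline summaries per arm that 10.6 does not request.

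**Step 5. Illustrate the precision of the missing table.** The documents give no SD for QTcF change, so 10 to 20 ms is assumed. SAP 3.6 gives 57 per arm after re-estimation. Removing the 10% dropout in the sample-size text gives 57 × 0.9 = 51.3, about 51. This is itself an assumption, because the Safety population counts everyone dosed at least once. The 95% half-width for one dose minus placebo is 1.96 × SD × √(2/n):

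- SD 10: 1.96 × 10 × √(2/51) = 3.9 ms
- SD 15: 1.96 × 15 × √(2/51) = 5.8 ms
- SD 20: 1.96 × 20 × √(2/51) = 7.8 ms

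Under these assumptions an observed difference of 10 ms would exclude zero throughout the range. The calculation shows what a change table could resolve. It does not show how often the category tables would miss such a shift.

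**The case against.** The strongest reply is that nothing has been withdrawn. Protocol section 14 calls the SAP a complement as well as the superseding document. SAP 10.6 does not say that its tables replace those of 14.4.4, and the two sets could stand side by side. SAP section 12 (changes from the protocol's analysis) and section 16 (the table index) are not visible, and the shells are a separate document. An interval table or a declared reason could be in any of these.

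This stands as a limit on the claim. A reader might infer that the interval summaries are lost. The documents do not support that: the measurements are still taken, an ECG listing is kept, and part of the SAP cannot be read. But 10.6 is not silent on ECG. It states its own, different analysis, so the superseding clause is the more natural reading, and two programmers could reasonably produce different outputs. Shells that may be revised separately from the SAP do not replace its text.

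Other inferences also go too far:

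- **That the ratings are the investigator's.** SAP 10.6 names no rater. Protocol 12.4 describes investigator review at Screening and a central cardiac laboratory, but does not say who rates the Day 7 and Day 14 tracings.
- **That a 10 ms shift would leave every patient rated normal.** The documents give neither a baseline QTcF distribution nor reading criteria. Entry is allowed up to just under 450 ms (men) or 470 ms (women), so some patients could cross a limit.
- **That a QT signal is expected.** Protocol 5.2.2 reports no significant ECG changes in Phase 1, with multiple doses up to 6 mg for 14 days.

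It is also fair to say that individual excursions have other routes into the report: the clinically significant category, discontinuation reasons and the listing. None of these shows a mean change.

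**Conclusion.** The mismatch between protocol 14.4.4 and SAP 10.6 is real and specific to ECG. As the visible SAP is written, no group-level summary of heart rate, PR, QRS, QT or QTcF is specified, either as observed values or as change from baseline. This includes the recordings in the estimated peak-concentration window.

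The conclusion rests on the visible text and on reading the precedence clause in its ordinary sense. It does not depend on the assumed SD or the figure of 51 per arm, which only illustrate precision. It would fall if section 12 or 16 of the SAP turned out to contain the interval tables; a reason given in section 12 would make the departure a declared one.

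No efficacy result, type I error or sample size is affected. The correction is worth making because it restores an explicit commitment on a safety endpoint at little cost.

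**What to change.** Add to SAP 10.6: descriptive statistics of observed values and change from baseline for heart rate, PR, QRS, QT and QTcF, by scheduled visit and treatment group, in the Safety population. Keep the frequency and shift tables. If the summaries are already in section 16, refer to them in 10.6. If they were omitted on purpose, say so in section 12 with the reason.

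Optionally, add counts by sex of patients reaching the QTcF values the protocol already names: 450 and 470 ms for men and 470 and 480 ms for women, from eligibility and withdrawal respectively. Protocol 14.4.4 does not promise this table. It would be descriptive only and would change no clinical rule.

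The cost is about two tables from data already collected, with no new measurements.
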